#### 4.1.3 Secondary Efficacy Endpoints

### **4.1.3.1** Improvement in Lequesne Hip index joint from baseline to 6 months post injection. (MON 18-01 only)

Since this is a secondary endpoint the data will be analyzed for each time point individually with no adjustments for multiplicity. Data will be analyzed via a one sample t-test on the difference between the month hip function score and the baseline hip function score. Formally, the hypothesis to be tested is:

```
H_0: \mu_{DMON} = 0 versus H_A: \mu_{DMON} > 0.
```

In this hypothesis,  $\mu_{DMON}$  is the mean change from baseline at a time point for Monovisc treated patients.

This will be analyzed using SAS PROC UNIVARIATE. ODS statements will be used to output the descriptive statistics and p-values into data sets that can be easily displayed using PROC REPORT.

This will be analyzed and tabled like the primary endpoint in section 4.1.2.1.

## **4.1.3.1** Improvement in DASH Shoulder index joint from baseline to 6 months post injection. (MON 18-02 only)

Since this is a secondary endpoint the data will be analyzed for each time point individually with no adjustments for multiplicity. Data will be analyzed via a one sample t-test on the difference between the month shoulder pain score and the baseline shoulder pain score. Formally, the hypothesis to be tested is:

$$H_0$$
:  $\mu_{DMON} = 0$  versus  $H_A$ :  $\mu_{DMON} > 0$ .

In this hypothesis,  $\mu_{DMON}$  is the mean change from baseline at a time point for Monovisc treated patients.

This will be analyzed using SAS PROC UNIVARIATE. ODS statements will be used to output the descriptive statistics and p-values into data sets that can be easily displayed using PROC REPORT.

This will be analyzed and tabled like the primary endpoint in section 4.1.2.1.

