6. ENDPOINTS

6.1 Primary Endpoint:

Reduction of index joint Numerical Rating Scale (NRS) pain from baseline to 6 Months post injection.

6.2 Secondary Endpoints:

- Improvement in DASH index joint from baseline to 6 months post injection.
- Improvement in Patient Global Assessment (PGA) from baseline to 6 months post injection.
- OMERACT-OARSI responder rate in the index joint at 6 months post injection.
- Time to treatment failure
- Reduction in Medication usage from baseline to 6 months post injection.

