7.3.7 Pain Assessment

Patient reported Pain of the index and contralateral shoulder joints will be measured with a Numerical Rating Scale (NRS).

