#### **SECONDARY ENDPOINTS:**

- Improvement in Lequesne Hip index joint from baseline to 6 months post injection. (MON 18-01 only)
- Improvement in DASH score for index joint from baseline to 6 months post injection (MON 18-02 only)

- Improvement in AOFAS index joint from baseline to 6 months post injection (MON 18-03 only).
- Improvement in Patient Global Assessment (PGA) from baseline to 6 months post injection.
- OMERACT-OARSI responder rate in the index joint at 6 months post injection.
- Time to treatment failure
- Reduction in Medication usage from baseline to 6 months post injection.

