#### 4.1.2 Primary Efficacy Endpoint

# 4.1.2.1 The mean change in index joint Pain from baseline to 6 Months as measured with NRS comparing the Monovisc treated group to baseline measurements.

The primary analysis will be the mean change in index joint pain from baseline to 6 months as measured by the Numerical Rating Scale.

The hypothesis to be tested is:

```
H_0: \mu_{DMON} = 0 versus H_A: \mu_{DMON} > 0.
```

In this hypothesis,  $\mu_{DMON}$  is the mean change in pain from baseline at 6 Months in MONOVISC treated patients.

The data will be analyzed via a one sample t-test.

This will be analyzed using SAS PROC UNIVARIATE. ODS statements will be used to output the descriptive statistics and p-values into data sets that can be easily displayed using PROC REPORT.

The tables for this analysis will be displayed as follows showing all time points for reference:

This analysis will be performed for each of the protocols

Summary of Differences in Mean Responses over time -

| Time Perios |                       |                 | Visit Result |                      |
|-------------|-----------------------|-----------------|--------------|----------------------|
|             | Descriptive Statistic | Baseline Result |              | Change from Baseline |
| 1 Week      | N                     |                 |              |                      |
|             | Mean                  |                 |              |                      |
|             | Std.Drv               |                 |              |                      |
|             | Median                |                 |              |                      |
|             | (Min,Max)             |                 |              |                      |
|             | p-value diff=0        |                 |              |                      |
| 1 Month     | N                     |                 |              |                      |
|             | Mean                  |                 |              |                      |
|             | Std.Drv               |                 |              |                      |
|             | Median                |                 |              |                      |
|             | (Min,Max)             |                 |              |                      |
|             | p-value diff=0        |                 |              |                      |

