## **4.1.3.2** Improvement in AOFAS index joint from baseline to 6 months post injection (MON 18-03 only).

Since this is a secondary endpoint the data will be analyzed for each time point individually with no adjustments for multiplicity. Data will be analyzed via a one sample t-test on the difference between the month ankle pain score and the baseline ankle pain score. Formally, the hypothesis to be tested is:

 $H_0$ :  $\mu_{DMON} = 0$  versus  $H_A$ :  $\mu_{DMON} > 0$ .

In this hypothesis,  $\mu_{DMON}$  is the mean change from baseline at the time points for Monovisc treated patients.

This will be analyzed using SAS PROC UNIVARIATE. ODS statements will be used to output the descriptive statistics and p-values into data sets that can be easily displayed using PROC REPORT.

This will be analyzed and tabled like the primary endpoint in section 4.1.2.1.

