### **4.1.3.3** The mean and percent change in Patient Global Assessment from Baseline to 1 Months, 3 Months and 6 Months.

Since this is a secondary endpoint the data will be analyzed for each time point individually with no adjustments for multiplicity. Data will be analyzed via a one sample t-test on the difference between the month PGA score and the baseline PGA score. Formally, the hypothesis to be tested is:

 $H_0$ :  $\mu_{DMON} = 0$  versus  $H_A$ :  $\mu_{DMON} > 0$ .

In this hypothesis,  $\mu_{DMON}$  is the mean change from baseline at the time points for Monovisc treated patients.

This will be analyzed using SAS PROC UNIVARIATE. ODS statements will be used to output the descriptive statistics and p-values into data sets that can be easily displayed using PROC REPORT.

This will be analyzed for each of the protocols and tabled like the primary endpoint in section 4.1.2.1.

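### SAP 4.1.3.1 is headed DASH but tests a shoulder pain score, its wording on change runs against its own hypothesis, and the signals on one- or two-sided testing conflict

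*SAP*

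**What the plan says.** **Endpoint.** Protocol 6.2 lists "Improvement in DASH index joint from baseline to 6 months post injection" as a secondary endpoint. The secondary endpoint list in SAP 3.0 names the DASH score for MON 18-02, and the shoulder section numbered 4.1.3.1 has DASH in its heading.

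**Variable tested.** Inside that section, the sentence that prescribes the analysis puts the t-test on "the difference between the month shoulder pain score and the baseline shoulder pain score".

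**Hypothesis.** SAP 4.1.2.1 (primary), 4.1.3.1 (DASH) and 4.1.3.3 (PGA) all test a mean of zero against a mean greater than zero. For the primary endpoint the parameter "is the mean change in pain from baseline at 6 Months in MONOVISC treated patients". No section prints a formula for change.

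**Level and p-value.** SAP 4.2 sets 5% for all tests and confidence intervals without saying one- or two-sided. The table shell in SAP 4.1.2.1, which the DASH and PGA sections adopt, labels its p-value row as a difference of zero.

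**Sample size.** Protocol 9.1 and SAP 4.1.1 assume a 2-point mean change on NRS, SD 2 to 2.5, 80% power and alpha 5%. They state 15 subjects required and at least 25 to be enrolled.

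**The concern.** DASH is the only function questionnaire in the Protocol 7.1 schedule and one of five secondary endpoints. A programmer who follows the SAP sentence rather than the heading would re-test the primary variable, and the function endpoint would have no prescribed test at any of the three follow-up visits.

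The other two matters concern how the hypothesis is carried out. If the DASH and PGA differences are computed in the order in which the sentences name the scores, a one-sided test against a mean above zero looks for worsening. And if the 5% is not assigned to one or two sides, a borderline primary result can be called significant or not according to a choice made at analysis.

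**Working it through.** **Step 1: the variable.** The four parallel secondary sections of the SAP, side by side:

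| SAP section | Heading names | Test sentence names |
|---|---|---|
| 4.1.3.1 (hip) | Lequesne | "the month hip function score and the baseline hip function score" |
| 4.1.3.1 (shoulder) | DASH | "the difference between the month shoulder pain score and the baseline shoulder pain score" |
| 4.1.3.2 (ankle) | AOFAS | "the difference between the month ankle pain score and the baseline ankle pain score" |
| 4.1.3.3 | PGA | "the difference between the month PGA score and the baseline PGA score" |

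The hip and PGA sentences fit their headings. The shoulder sentence does not. Protocol 7.3.7 and Appendix 1 measure shoulder pain by NRS. DASH (Appendix 2) is a 30-item questionnaire in which only items 24, 25 and 29 ask about pain, and neither document calls it a pain score. The ankle sentence shows the same pattern, but the ankle protocol is not among these documents, so it cannot be checked here.

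**Step 2: the sign.** In Appendices 1, 2 and 3, higher is worse on NRS, DASH and PGA.

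- *DASH and PGA.* The sentences name month, then baseline. Taken in that order, D = month − baseline, so improvement gives D < 0 and the alternative (mean > 0) describes worsening.
- *NRS.* Protocol 9.1 and SAP 4.1.1 treat a 2-point change as improvement, and the endpoint is worded as a reduction. With an alternative above zero, this implies D = baseline − visit.

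For scale, suppose the mean improvement is four standard errors with 25 subjects (24 df). With D = baseline − visit, t = +4.00 and the upper-tail p is 0.0003. With D = month − baseline, t = −4.00 and the upper-tail p is 0.9997. The two-sided p is 0.0005 either way, so the sign affects the p-value only if the test is one-sided.

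**Step 3: sidedness, starting from the plan's own 15.** Inputs from SAP 4.1.1: δ = 2, SD 2 to 2.5, alpha 5%, power 80%. The method is the exact one-sample t-test with noncentrality δ√n/SD. At n = 15 and SD 2.5 this is 2 × √15 / 2.5 = 3.10.

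| SD | Two-sided 5%: n for 80% | One-sided 5%: n for 80% |
|---|---|---|
| 2.0 | 10 | 8 |
| 2.25 | 12 | 10 |
| 2.5 | **15** (82.1%; n = 14 gives 79.0%) | 12 (82.9%; n = 11 gives 79.5%) |

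The stated 15 is reproduced exactly by two-sided 5% at SD 2.5 and by no one-sided case. The directional alternative therefore disagrees with the sample size, and the p-value row for a difference of zero is non-directional.

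**Step 4: where the two readings part for the primary test.** The smallest observed mean reduction that is significant is t × SD/√n, with t at the 0.95 (one-sided) or 0.975 (two-sided) quantile. At n = 25 and SD 2.5, SD/√n = 0.5, giving 1.711 × 0.5 = 0.86 and 2.064 × 0.5 = 1.03. The number evaluable at 6 months is unknown, so three values are shown:

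| n | SD 2.5: one-sided to two-sided | SD 2.0: one-sided to two-sided |
|---|---|---|
| 15 | 1.14 to 1.38 | 0.91 to 1.11 |
| 20 | 0.97 to 1.17 | 0.77 to 0.94 |
| 25 | 0.86 to 1.03 | 0.68 to 0.83 |

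The readings disagree only inside these bands. For example, a mean reduction of 0.95 at n = 25 and SD 2.5 gives one-sided p = 0.035 and two-sided p = 0.070.

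**Step 5: power.** At SD 2.5, two-sided power is 82.1%, 92.4% and 97.0% at n = 15, 20 and 25. One-sided power is 90.3% at 15 and 98.7% at 25.

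**The case against.** The best defence is that this is a drafting slip whose intent is plain. The section heading and the SAP 3.0 endpoint list both name DASH. The sentence does not say NRS, and a shoulder pain score is not a defined term. Someone working under a DASH heading is unlikely to rerun the NRS analysis. That stands as to intent and lowers the risk. It does not repair the sentence, which is the only instruction on what to test and names something that the protocol measures with another instrument.

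On sign, the phrase about a difference between two scores is not a formula, and the word improvement in the endpoint shows the direction wanted. That too is fair, but it leaves the programmer to infer the direction, and the written order points the other way.

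On sidedness, the p-value label may do no more than name the null hypothesis. Agreed: it settles nothing alone. It is one of several signals that do not agree.

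Three stronger readings are tempting, and the documents do not support them:

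- *A reader might infer that the plan drops DASH.* The heading and both endpoint lists contradict that.
- *A reader might infer that the primary NRS test is aimed at worsening.* The sample-size text and the reduction wording imply that positive change is improvement for NRS. The conflict sits in the DASH and PGA sections.
- *A reader might infer that the trial is too small.* Fifteen subjects suffice under either sidedness.

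**Conclusion.** The analysis rule for DASH is wrong as written: heading and endpoint list say one thing, and the test sentence another. It affects one of five secondary endpoints at all three follow-up visits. The implied sign for DASH and PGA opposes the stated alternative when the sentences are read in written order. Sidedness is contradictory rather than merely absent: a directional alternative, a non-directional p-value row, a 5% without sides, and an n of 15 that fits only a two-sided test at the upper end of the assumed SD range.

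The practical effect is small. The disputed band for the primary result is about 0.15 to 0.25 points wide and lies wholly below the assumed 2-point change in every case shown. The sign has no effect on a two-sided p-value.

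These figures rest on the plan's NRS assumptions (δ = 2, SD 2 to 2.5) and on assumed evaluable numbers of 15, 20 and 25. The documents give no DASH effect or SD, so nothing here measures power for DASH.

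**What to change.** In the SAP, before analysis:

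1. In 4.1.3.1 (MON 18-02), replace the shoulder pain score with the DASH score in both places in the test sentence.
2. Add one sentence: for MON 18-02, D = baseline minus visit for NRS, DASH and PGA, so that a positive value is improvement.
3. State that reported p-values are two-sided at 5%, and write the alternative as a mean not equal to zero. This keeps the stated 15 and agrees with the p-value row in the table shell.
4. Check the AOFAS sentence in 4.1.3.2 against the ankle protocol.

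The cost is SAP wording only; the 15 required and 25 enrolled do not change. The one downside of two-sided testing is a slightly stricter threshold: an observed NRS reduction of 1.03 rather than 0.86 points at n = 25 and SD 2.5. Protocol 9.1 carries the same directional alternative. Aligning it needs an amendment under Protocol 13.3, which can wait for the next one if the SAP states the clarification.

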## **4.1.3.2** Improvement in AOFAS index joint from baseline to 6 months post injection (MON 18-03 only).

Since this is a secondary endpoint the data will be analyzed for each time point individually with no adjustments for multiplicity. Data will be analyzed via a one sample t-test on the difference between the month ankle pain score and the baseline ankle pain score. Formally, the hypothesis to be tested is:

 $H_0$ :  $\mu_{DMON} = 0$  versus  $H_A$ :  $\mu_{DMON} > 0$ .

In this hypothesis,  $\mu_{DMON}$  is the mean change from baseline at the time points for Monovisc treated patients.

This will be analyzed using SAS PROC UNIVARIATE. ODS statements will be used to output the descriptive statistics and p-values into data sets that can be easily displayed using PROC REPORT.

This will be analyzed and tabled like the primary endpoint in section 4.1.2.1.

### **4.1.3.3** The mean and percent change in Patient Global Assessment from Baseline to 1 Months, 3 Months and 6 Months.

Since this is a secondary endpoint the data will be analyzed for each time point individually with no adjustments for multiplicity. Data will be analyzed via a one sample t-test on the difference between the month PGA score and the baseline PGA score. Formally, the hypothesis to be tested is:

 $H_0$ :  $\mu_{DMON} = 0$  versus  $H_A$ :  $\mu_{DMON} > 0$ .

In this hypothesis,  $\mu_{DMON}$  is the mean change from baseline at the time points for Monovisc treated patients.

This will be analyzed using SAS PROC UNIVARIATE. ODS statements will be used to output the descriptive statistics and p-values into data sets that can be easily displayed using PROC REPORT.

This will be analyzed for each of the protocols and tabled like the primary endpoint in section 4.1.2.1.

### **4.1.3.4** Responder index based on OMERACT- OARSI responder index at 1 Month, 3 Months and 6 Months.

The response rate for each time point will be tabulated and exact 95% confidence intervals will be calculated.

This will be estimated and tested using PROC FREQ with the BINOMIAL option. The results will be displayed similar to the format below.

Summary of the OMERACT-OARSI Responder Rates at each visit and each protocol.

| Parameter               | 1 Week | 1 Month | 3 Months | 6 Months |
|-------------------------|--------|---------|----------|----------|
| Estimate n/N (%)        |        |         |          |          |
| 95% Confidence Interval |        |         |          |          |

#### 4.1.3.5 Time to Treatment Failure.

The time to treatment failure will be assessed via the estimation of the Kaplan-Meier curve. This will be done via the PROC LIFEREG procedure in SAS. The estimate of the median survival time and the 95% confidence intervals will be reported. This will be done for each protocol.

For all studies, a patient is considered a treatment failure if any of the following occur:

Corticosteroid injections
Shock-wave therapy
Dry Needling
Nitroglycerin patches
Prolotherapy (PrT).
Platelet / PRP / BMAC injection
Hyaluronic Acid.
Surgical treatment – open or arthroscopic

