#### 2.0 Study Design

This is a prospective, post market clinical follow-up (PMCF) multi-center, open-label study to evaluate the residual risk of injections of MONOVISC for relief of pain in patients with a diagnosis of an osteoarthritic hip joint (MON 18-01), shoulder joint (MON 18-02), and ankle joint (MON 18-03).

The subjects in each of these study will be patients with a diagnosis of osteoarthritic (OA) joint who the investigator determines are appropriate candidates for treatment with a viscoelastic injection of MONOVISC.

In each study, up to 25 subjects will be enrolled at up to 20 investigational sites in the EU. Subject participation will last approximately 6 Months, with visits scheduled at Screening, Baseline, 1 month, 3 month and 6 months.

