#### **EXPLORATORY ENDPOINTS**

Any comparisons across timepoints (baseline to 6 months) not described in the primary or secondary endpoints, including but not limited to:

- Demographics
- Medical History
- History of joint osteoarthritis
- Rescue Medication Use
- Treatment Failure
- Injection procedure
- Concomitant medications
- Non-drug therapy

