#### 4.1.4 Exploratory Endpoints

Any comparisons across timepoints (baseline to 6 months) not described in the primary or secondary endpoints, including but not limited to:

- Demographics:
  - o Male vs Female
  - Age  $\leq$ 50 years vs > 50 years
- Medical History
  - With / without history of joint surgery
- History of joint osteoarthritis
  - With / without prior joint pathologies
- Injection procedure:
  - With / without guidance
- Concomitant medications
- Non-drug therapy
  - o With / without non-drug therapy

Specifically, subset populations will be compared based on the primary endpoint result and OMAREACT OARSI responder index at 6 months for each subset.

For the exploratory analyses, the continuous variables will be summarized via descriptive statistics (n, mean, median, standard deviation, minimum, and maximum. The discrete variables will be summarized via counts and percents.

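### Time to treatment failure is planned as a Kaplan-Meier analysis but assigned to a parametric procedure with no distribution named, and its only stated number, the median, is unlikely to be reached unless about half the subjects fail

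*SAP*

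**What the plan says.** Time to treatment failure is a secondary endpoint in Protocol 6.2 and in SAP 3.0. The protocol gives no method for it. SAP 4.1.3.5 gives three instructions in succession:

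- the estimator: "The time to treatment failure will be assessed via the estimation of the Kaplan-Meier curve";
- the software: "This will be done via the PROC LIFEREG procedure in SAS";
- the reported result: "The estimate of the median survival time and the 95% confidence intervals will be reported".

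The event is defined by a list: "a patient is considered a treatment failure if any of the following occur", followed by eight interventions. The section names no survival distribution, time origin, censoring rule or convention for a median that is not reached.

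On size and follow-up, SAP 2.0 says "In each study, up to 25 subjects will be enrolled at up to 20 investigational sites in the EU" and "Subject participation will last approximately 6 Months". SAP 3.0 also lists "Treatment Failure" among the exploratory endpoints. The itemised list in SAP 4.1.4 leaves it out, but a general sentence there could cover it: "The discrete variables will be summarized via counts and percents".

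**The concern.** Kaplan-Meier estimation is non-parametric. PROC LIFEREG fits a parametric model, and its quantiles come from the fitted distribution. A programmer who follows the estimator and one who follows the procedure will report different things.

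- **Following the estimator:** the median is undefined unless the curve falls to 50% within about 6 months. Apart from the curve itself, the median is the only number that SAP 4.1.3.5 asks for.
- **Following the procedure:** a median can be printed when few subjects fail. If it exceeds about 6 months it is an extrapolation, and its value depends on a distribution that nobody chose in advance.

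The same data could therefore be reported as 'not reached' or as a median of well over a year. The SAP's stated aim concerns relief up to 6 months. SAP 4.1.3.5 applies to all three studies that the SAP covers, so any misreading would be repeated.

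**Working it through.** The plan states no figure for this endpoint, so there is none to reproduce. The only calculated figure in the documents is the 15 subjects for the primary t-test. It reproduces (two-sided 5%, SD 2.5, exact t power 82.1%) and has no bearing here.

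**Inputs.** n = 25 per study (SAP 2.0 and 4.1.1) and follow-up of about 6 months (SAP 2.0). The documents give no 6-month failure rate p, so a range is assumed.

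**1. When the Kaplan-Meier median exists.** With no censoring before 6 months, the curve after d failures stands at (25 − d)/25. After 12 failures it is 13/25 = 0.52, and after 13 it is 12/25 = 0.48. At least 13 failures are needed, so the chance of reaching the median is P(X ≥ 13) with X ~ Binomial(25, p). The last column adds 20% dropout spread uniformly over 6 months (assumed), with exponential failure times and 40,000 simulated trials per rate.

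| Assumed 6-month failure rate | No early censoring | 20% dropout |
|---|---|---|
| 20% | 0.04% | 0.07% |
| 30% | 1.7% | 2.4% |
| 40% | 15% | 17% |
| 50% | 50% | 50% |
| 60% | 85% | 83% |

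**2. When its upper confidence limit exists.** Inverting the pointwise Greenwood interval, the distance of the curve from 0.5 is z = 1.93 (linear) or 1.94 (log-log) after 17 failures, and 2.45 or 2.41 after 18. Against 1.96, a finite upper 95% limit needs about 18 of 25 failures (72%).

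**3. What a parametric median would be.** Fix only the 6-month survival at 1 − p.

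- Weibull with shape k: median = 6 × [ln 2 / (−ln(1 − p))]^(1/k). At p = 20% this gives 30.3, 18.6 and 12.8 months for k = 0.7, 1 and 1.5.
- Lognormal with scale σ: median = 6 × exp(−σ × Φ⁻¹(p)). At p = 20% this gives 11.8 and 16.5 months for σ = 0.8 and 1.2.

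At p = 10% the same set runs from 16.7 to 88.5 months.

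**4. One data set, four models (illustration only).** Suppose 3 of 25 fail, at 2, 3.5 and 5 months, and the other 22 are censored at 6 months.

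- Exponential: exposure = 2 + 3.5 + 5 + 22 × 6 = 142.5 months; rate = 3/142.5 = 0.0211; median = ln 2 / rate = 32.9 months; 95% CI = 32.9 × exp(±1.96/√3) = 10.6 to 102.
- Weibull by maximum likelihood: shape 1.71, median 16.0 months, 95% CI 4.4 to 58.7.
- Log-logistic: 18.3 months. Lognormal: 22.9 months.
- Kaplan-Meier: median not reached. Failure-free probability at 6 months = 22/25 = 0.88. The standard error on the log-log scale is √[3/(25 × 22)] / |ln 0.88| = 0.0739/0.1278 = 0.578, and exp(1.96 × 0.578) = 3.10. The 95% CI is therefore 0.88^3.10 to 0.88^(1/3.10) = 0.67 to 0.96.

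**The case against.** The strongest reply is that the estimator is stated plainly and only the procedure name is wrong. With no distribution or covariate mentioned, LIFEREG looks like a slip for LIFETEST, and a programmer would probably notice. That may well be how it arose. The sentence is still an operative instruction in the analysis plan, and carried out literally it gives a different number.

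A second reply is that LIFEREG run without a named distribution falls back on its software default (Weibull), so a literal reading gives one median, not four. That narrows the spread in the illustration. It leaves the extrapolation in place and means the distribution is chosen by default, not by the plan.

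Third, 'not reached' is a valid Kaplan-Meier result, and that it needs about half the subjects to fail is close to the definition of a median. This is correct. The difficulty is that no other number is specified for the endpoint. The curve can be read at any time, but SAP 4.1.3.5 asks for no estimate with a confidence interval at a fixed time. The counts and percents available through SAP 4.1.4 do not allow for dropout.

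Fourth, Protocol 7.4 makes the injection visit Day 0, so the time origin is easily inferred. That stands, and the missing censoring rule is the larger gap. Finally, the Month 6 visit may fall 7 days early (Protocol 7.1), so the fixed times need defining.

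**Conclusion.** The concern holds. SAP 4.1.3.5 assigns a non-parametric estimate to a parametric procedure with no distribution named, and this is true at any failure rate.

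How often the median is missed depends on a failure rate that the documents do not give. At n = 25 without early censoring, the chance of reaching it is below 2% for rates up to 30% and reaches 50% only when half the subjects fail; 20% dropout changes this little. The range of 16 to 33 months rests on an invented data set and shows only how much the choice of distribution matters.

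The endpoint is secondary and descriptive. The primary t-test, the sample size and the safety analyses are not affected. The correction should be made before the analysis is programmed.

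**What to change.** Amend SAP 4.1.3.5 as follows:

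- Replace PROC LIFEREG with PROC LIFETEST (product-limit estimate).
- Measure time from injection to the first listed failure event, and censor subjects without an event at last contact.
- Report the Kaplan-Meier failure-free probability with 95% CI at 1, 3 and 6 months. Name the study day used for each time, given the visit windows, and the interval method (for example log-log).
- Report the median with its CI only if the curve reaches 50%; otherwise state 'not reached'.

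The cost is one SAP paragraph and a change of procedure. No new data are needed, and the list of failure events is unchanged.
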